9.3.3 Other Variables and Covariates

Table 6. Variable categories and data sources

Variables	Categories	Data source	Comment
Age	Different categorizations may be used -12 <50; 50-<65; 65-<70; 70-<80; 80+ -18-<40; 40-<50; 50+; 65+; 70+; 80+	GDPPR	BMI is binary as obese or not using HES, SUS, GDPPR or BMI can be created from weight/height if
Gender	Male/Female	-	available;
Ethnicity	White, Black, Asian, Other, Mixed		
Region	NHS Region	-	
Sociodemographic	Socioeconomic status – Index of Multiple Deprivation (IMD)		
BMI	-Obese (BMI 30+) -Not-obese (BMI <30)		
Smoking	- Current - Past - Non smoker		
Comorbidity	Specific comorbidities known to relate with increased risk of severe COVID- 19 and/or suboptimal vaccine response and/or vaccine contraindication including chronic respiratory disease, chronic kidney disease, chronic heart disease and vascular disease, chronic liver disease, chronic neurological disease, diabetes mellitus, severe mental illness, morbid obesity, asplenia or dysfunction of the spleen, and immunosuppression due to disease or treatment.	ORCIHD, HES and GDPPR	Follow JCVI/Green book list of comorbidities (COVID-19 Greenbook chapter 14a) Using ICD or SNOMED codes to identify comorbidities during the baseline period. For immunosuppressant medications, see Prescribed medication section below.
CMMS	0, and by quartile		Created from specific comorbidities;
Non-COVID-19 vaccination	 Flu vaccination (Y/N) Receive adequate vaccination (Y/N) 	GDPPR	An algorithm will be developed to determine if an individual is adequately vaccinated according to recommended vaccination schedule by age and comorbidity status
Prescription medication	Immunosuppressant vs. not	GDPPR	Prescribed medications at baseline will be grouped into immunosuppressant or not.
LTC /assisted living care facility	Yes/No	Not in any database	To be created for people aged 70+ by comparing their zip codes and LTC

Variables	Categories	Data	Comment
		source	
			address; or vaccination at LTC facility. (ORCHID)
Household composition	Size and age combination.	ORCHID UKHSA VE cohort	Available for 7.2 million subset of ORCHID
Frailty score	eFI grouped into - Mild - Moderate - Severe	Derived from GDPPR	Use an algorithm already developed to derive eFI, only available for population 65years and older. For this sub-group analysis.

BMI: body mass index; CMMS: Cambridge Multimorbidity Score; eFI: electronic frailty index; GDPPR: General Practice Extraction Service data for pandemic planning and research; HES: Hospital Episode Statistics; JCVI: Joint Committee on Vaccination and Immunisation; LTC: long term care; ORCHID: Oxford-Royal College of General Practitioners Clinical Informatics Digital Hub; SUS: Secondary Uses Service; UKHSA: UK Health Security Agency; VE: vaccine effectiveness.

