9.7 Data Analysis

9.7.1 Statistical Methods – General Aspects

A detailed SAP will be developed for this analysis. The SAP may modify the plans outlined in the protocol; any major modifications of primary endpoint definitions or their analyses would be reflected in a protocol amendment. For all study designs, p-values will be quoted to two decimal places, unless they are less than 0.001 (whereby the p-value will be given as < 0.001) or between < 0.005 and > 0.001, in which case they will be stated to three decimal places. Parameter estimates will be reported with 95% CIs. All statistical tests are 2 sided and with a 5% significance level.

A CONSORT 2010 Flow Diagram of the study population detailing each step of the inclusion and exclusion criteria applied will be generated. As indicated in section 9.4, to obtain the most followup data, the primary analysis will include all HES data until 8 weeks prior and all raw hospitalization data (SUS) from 8 weeks to 2 weeks prior database lock. A sensitivity analysis including only HES data, therefore a shorter follow-up for hospitalization, will also be done.

For the concurrent control arm, each week starting from 8th December 2020, we will match all newly vaccinated persons in a 1:1 ratio to unvaccinated controls (Dagan et al, 2021). Newly vaccinated persons will be eligible for inclusion in the study, even if they will have previously been selected as a control. We will match vaccine recipients and controls on variables associated with the probability of both vaccination and infection or severity of COVID-19: age (study defined age bands), gender, general practice, (or NHS Region), and comorbidity as defined by CMMS quartile. We will exact match each week (if feasible). To assess the quality of matching, love plots will be created showing the mean standardized difference between each vaccinated cohort (AstraZeneca or other vaccine cohort) and the comparator cohorts in participants' characteristics. If important differences are observed, the matching criteria will be refined.

The demographic and characteristics of study participants in each vaccine arm and its respective control arm at baseline will be determined during the 12-month period before index date using the measurement closest to index date.

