Summary tables of all patient characteristics and end points indicated in section 9.3.2 will be created for both the before and after matching situation to provide insight in population characteristics as well as in errors and missingness. Categorical variables will be checked on meaningful categories and frequencies. It is not anticipated that categories will have too low frequency. Pooling will be considered when the frequency for a category becomes below 1000.

Continuous variables will be summarized in terms of min, max, interquartile range, median and mean to get insight in these variables, but also to provide a first indication of use of same unit across the database and to obtain a first impression about possible transformations needed. Missing values will be considered in detail. If the percentage of missingness is below 10%, complete case analyses will be performed. When exceeding 10%, multiple imputation will be run additionally based on the total dataset.

For each outcome event, the summary tables will present for each study cohort the number of first events, total person-years for the event and number of first events per person-years (rate), the RR and the VE which is calculated as 1 - RR. This will also be provided per age group and per frailty score where further stratification/subgroups are indicated below. Finally, VE will also be provided in shorter periods after dose 1, and between the doses, and presence of comorbidities.

Poisson regression with offset for time at risk will be used to estimate rates using the matched dataset, adjusting for the matching variables and BMI, smoking, prescribed medications, and frailty score, which are known to increase risk of hospitalization and death and are likely associated with vaccination.

Checks on linearity for continuous variables will be performed. In order to evaluate interactions of independent variables with the exposure (i.e. vaccinated/comparator), continuous variables will be categorized and the VE will be tabulated per category. For variables for which the maximum and minimum VE across categories is more than 10% different, interaction effects with the exposure will be taken into account in the Poisson model. For interactions among independent variables that are not the exposure, interaction variables will be created. Forward selection is performed, and interaction variables will be included when the computed VE changes with more than 10%.

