9.7.2 Stratification/Subgroup Analyses

Stratifications/subgroup analyses will be fully detailed in the SAP, and may include:

- Age: <12, 12-16, 16-49, 50-64, 65-69, 70-79, 80+; or 16-39, 40-<49, 50+, 65+, 80+
- Comorbidity
 - o categories of the CMMS
 - specific comorbidities known to indicate high risk for COVID-19 infections and/or suboptimal response to vaccine, in accordance with National guidance from UK Health Security Agency (UKHSA, 2021) or other, including chronic respiratory disease, chronic kidney disease, chronic heart disease and vascular disease, chronic liver disease, chronic neurological disease, diabetes mellitus, severe mental illness, morbid obesity, asplenia or dysfunction of the spleen, and immunosuppression due to disease or treatment.
- Immunosuppressant prescribed medication: current vs. past use, regimen
- Long-term care or assisted living care residents (if possible)

Stratifications/subgroups in the vaccinated population may include:

- Heterologous dosing
- Vaccine dose: people receiving 1 dose only, ≥1 dose, 2 doses, booster/other additional doses
- Intervals after the 1st dose among people receiving 1 dose only: 0-7, 8-14, 15-21, 22-28, 29-35, 36-42, 43-49, 50-70, 71-77, 78-84 days post dose 1, and/or other combinations may be used
- Interval between doses among people receiving 2 (or more) doses: 21 to 41, 42 to 69, 70 to 77, 78 to 84, over 84 days and/or other combinations may be used.
- Vaccine batch number
- Aged over 65 by electronic frailty index (eFI) categories (mild, moderately, and severely frail)

Stratification/subgroups in the population with COVID-19 may include:

- COVID-19 severity
- COVID-19 variant

Subgroup analyses will only be conducted if sufficient events for an outcome within the subgroup allows.

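### BMI enters the VE model as one cut at 30, and morbid obesity, captured separately in Table 6, has no named term there, so some residual confounding, probably small, is possible

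*Protocol*

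**What the plan says.** - **BMI coding (9.3.3, Table 6).** The categories column gives "Obese (BMI 30+) -Not-obese (BMI <30"). The comment column repeats the binary form and allows BMI to be built from weight and height where these exist: "BMI is binary as obese or not using HES, SUS, GDPPR or BMI can be created from weight/height if" available. The age row of the same table leaves its bands open; the BMI row does not.
- **Primary model (9.7.1).** Poisson regression on the matched data, "adjusting for the matching variables and BMI, smoking, prescribed medications, and frailty score". The stated reason for these covariates is that they are factors "which are known to increase risk of hospitalization and death and are likely associated with vaccination".
- **Morbid obesity.** Table 6 lists it as a separate comorbidity ("diabetes mellitus, severe mental illness, morbid obesity, asplenia or dysfunction of the spleen"). Section 9.7.2 includes it among the "specific comorbidities known to indicate high risk for COVID-19 infections and/or suboptimal response to vaccine" that may define subgroups. It is not named in the 9.7.1 model.
- **Comorbidity in matching, and so in the model (9.7.1).** "general practice, (or NHS Region), and comorbidity as defined by CMMS quartile". Table 6 says the CMMS is created from specific comorbidities but does not list them.

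**The concern.** By the reasoning in 9.7.1, BMI is a confounder, being linked to both outcome and vaccination. A single cut at 30 controls only the contrast across that cut. Above it, people with morbid obesity share a level with all other obese people, although the protocol treats morbid obesity as a distinct high-risk condition. Below it, underweight is not separated from normal weight. A CMMS quartile cannot isolate one condition, and the protocol does not say whether morbid obesity feeds the score at all.

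Two planned checks are weakened. The linearity checks for continuous variables in 9.7.1 do not reach a BMI that has already been dichotomised. A love plot of binary BMI cannot show imbalance inside either level.

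At stake is a systematic shift in the primary VE. Section 9.5 counts more than 7 million Oxford/AstraZeneca recipients, so random error in the main estimates should be small and the confidence interval would not signal such a shift.

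**Working it through.** The protocol states no figure on this point, so there is nothing to reproduce. The calculation below only gauges size, and **every input to it is an assumption**.

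**Formulas.** Within one BMI level, let a subgroup U have prevalence p_c in controls, odds ratio OR for being vaccinated versus control, and k times the event rate of the rest of the level.

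1. Prevalence in the vaccinated: p_v = o/(1+o), where o = OR × p_c/(1−p_c).
2. Bias factor on the rate ratio: B = [1+p_v(k−1)] / [1+p_c(k−1)].
3. Whole cohort, approximately: B_all = w × B_obese + (1−w) × B_non-obese, with w the obese share of events (0.25 to 0.5).
4. Apparent VE = 1 − (1−VE) × B_all.

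**Worked example (moderate inputs).**

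- Morbid obesity within the obese: p_c = 0.10, OR = 1.5, k = 2. Then o = 0.1667, p_v = 0.1429, and B = 1.1429/1.10 = 1.039.
- Underweight within the non-obese: p_c = 0.02, OR = 0.67, k = 2. Then o = 0.01367, p_v = 0.01349, and B = 1.01349/1.02 = 0.9936.
- With w = 0.4: B_all = 0.4 × 1.039 + 0.6 × 0.9936 = 1.0118. A true VE of 80% appears as 1 − 0.2 × 1.0118 = 79.76%.

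**Apparent VE (%) for the whole cohort when the true VE is 80%**

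| Morbid obesity in the obese (p_c, OR, k) | Underweight in the non-obese (p_c, OR, k) | w=0.25 | w=0.4 | w=0.5 |
|---|---|---|---|---|
| 0.10, 1.25, 1.5 | 0.02, 0.8, 1.5 | 79.98 | 79.94 | 79.91 |
| 0.10, 1.5, 2 | 0.02, 0.67, 2 | 79.90 | 79.76 | 79.67 |
| 0.15, 2, 2 | balanced | 79.52 | 79.23 | 79.04 |
| 0.15, 2, 3 | balanced | 79.15 | 78.64 | 78.29 |
| 0.15, 3, 3 | balanced | 78.49 | 77.59 | 76.98 |
| balanced | 0.04, 0.33, 3 | 80.73 | 80.59 | 80.49 |

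**Reading the table.**

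- The two moderate rows shift VE by 0.02 to 0.33 points.
- Doubled odds with k = 2 shift it by 0.5 to 1.0 points. With k = 3 and an OR of 2 to 3, the shift is about 0.9 to 3.0 points.
- The last row moves the other way, by 0.5 to 0.7 points. The two pooled groups can therefore offset each other.
- The shift in VE points is proportional to 1−VE. For B_all = 1.0163 (second row, w = 0.5), a true VE of 60% appears as 59.35% and a true VE of 90% as 89.84%.

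**The case against.** The strongest reply is that this is a preference about coding. Several safeguards exist. Arms are matched 1:1 on age, gender, practice or region, and CMMS quartile. The model adjusts for frailty. Patient characteristics are tabulated before and after matching. Love plots are planned, and matching is refined if important differences appear. Morbid obesity is captured from codes and is a candidate VE subgroup. The SAP, which is not shown, may modify the plan and could set a finer coding.

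Much of this stands, and it is why the point is minor. A large imbalance in morbid obesity would be visible if its flag is plotted, but the protocol does not say that it will be. Table 6 does commit to the binary form, so finer coding would change a stated method.

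Three stronger readings are tempting, and the documents do not support them:

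- **Unrecorded BMI counts as not obese.** The protocol never says so. Table 6 defines not obese by a BMI below 30, and 9.7.1 has a rule for missing values: complete-case analysis below 10% missing, multiple imputation in addition above that. The protocol is merely silent on how that rule meets a variable that can rest on codes.
- **Pooling underweight with normal weight inflates VE at older ages.** Frailty score is in the model and is available from age 65, and CMMS is matched, so much of what underweight marks there may already be adjusted for.
- **VE is biased down in the young and up in the old.** Section 9.1 says that people aged 16 to 64 with comorbidities were recommended early vaccination. It does not mention BMI. Weekly matching also continues well beyond the early roll-out.

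**Conclusion.** The point holds as a minor weakness. The BMI term in the primary VE model is fixed at one cut, and a high-risk condition that the protocol already captures has no named term there. Residual confounding within the two BMI levels is possible, but neither its direction nor its size follows from the protocol. Under the assumed inputs it is probably small: below 0.5 VE points at a true VE of 80% for moderate imbalance, and about 1 to 3 points only if strong imbalance survives matching and the risk ratios are also strong. A reader might infer that the primary VE, or VE by age group, is materially distorted; nothing in the protocol establishes that.

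**What to change.** In Table 6 and the 9.7.1 model:

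1. Add the existing morbid-obesity flag as a separate level of the BMI variable or as its own term.
2. Where a BMI value, or weight and height, exists, replace the single cut at 30 with finer BMI categories or a spline.
3. Include the flag and the finer BMI variable in the love plots.
4. State that people with neither a BMI value nor a relevant code are handled under the 9.7.1 missing-data rule.

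The cost model in 9.7.6.2 also adjusts for BMI status and could take the same definition. No new data source is needed. The cost is slightly more derivation work and possibly more missing BMI, which may pass the 10% threshold and trigger the planned multiple imputation.

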9.4 Data Source(s)

This study will employ linked England's national databases for data on background characteristics, medications, comorbidities, COVID-19 infection status, vaccination status, hospitalization, ICU admission, and mortality. The datasets use unique identifiers allowing linkage across the datasets and avoidance of duplicates.

Through the NHS DARS it is possible to request access to a number of secondary data assets collected as part of routine care and commissioning activities in the NHS. With appropriate approval, these data assets are linkable in their TRE. Data assets available through DARS which may be used for this study include:

- General Practice Extraction Service (GPES) data for pandemic planning and research (GDPPR): central collection of GP patient data for COVID-19 purposes (fortnightly collection – All GP practices in England). Limitations of these data included: (1) Some practices may have poor data quality; (2) The clinical data are restricted to 56,318 concepts from the much larger SNOMED clinical terminology (SNOMED CT international version has 352,567 concepts, the UK version has additional concepts to meet national needs)(SNOMED, 2020). Careful testing will be required for the equivalence of variables between ORCHID and GDPPR. We will carefully compare descriptive statics for key variables, some measures such as Cambridge Multimorbidity Score (CMMS) will require careful validation in GDPPR as some of their component codes do not exist within GDPPR.
- NIMS includes 2 associated datasets including COVID-19 Vaccination Status and COVID-19 Adverse Reaction.
- HES: this is the transformed data, initially part of the Commissioning Data Set (CDS), covering patients attending accident and emergency (A&E) units, admitted for treatment,

or attending outpatient clinics at NHS hospitals in England, including details about length of stay and HRG to enable health economic analysis. An HRG is a grouping consisting of patient events that have been judged to consume a similar level of resource, which can be linked to an appropriate NHS tariff. Statistical controls have been applied to the HES products. Data on cost will be extracted from HES using HRG. (Time lag 8-12 weeks)

- ECDS: this collects data from A&E Departments (time lag 8-12 weeks). Only available for linkage to ORCHID.
- Civil Registrations (Deaths): Information including the date, place and certificated cause of death from the Office for National Statistics (ONS) (Time lag 8-12 weeks, released by NHS Digital with HES)
- COVID-19 SGSS Demographic and diagnostic information from laboratory test reports for patients tested for COVID-19 in England only. It currently includes the first positive results from pillar 1 (swab testing in Public Health England (PHE) and NHS hospital labs and pillar 2 (swab testing for the wider population) (Time lag less than 1 week)
- COVID-19 UK Non-hospital Antigen Testing Results (Pillar 2) data includes a range of COVID19 test results, including NPEX. This is broadly similar to SGSS, but only covers Pillar 2 data, however, contains the full result set i.e. all positive, negative and null results.
- COVID-19 Hospitalization in England Surveillance System (COVID-19 SARI-Watch/CHESS): Epidemiological data on COVID-19 infection in persons requiring hospitalization in ICU or High Dependency Units. It records all demographic, risk factor, treatment and outcome information for patients admitted to hospital with a confirmed COVID-19 diagnosis. This only has data from a limited number of surveillance hospitals. (Time lag – less than 1 week)
- SUS Episodes (including the following concepts: Admitted Patient Care (APC), Outpatient, Critical Care & A&E). This covers all secondary care provided in England and paid for by the NHS. This is essentially the CDS. These data are transformed to create HES product set that is subject to official publication timelines. Therefore, SUS should be considered tactical but carries a shorter latency (Time lag –1-2 weeks). Only available for linkage to ORCIHD.
- ORCHID a TRE for research and surveillance (de Lusignan, 2021). This TRE contains the Oxford-Royal College of General Practitioners (RCGP) Research and Surveillance Centre (RSC) one of Europe's oldest sentinel systems. The network has been expanded considerably during the SARS-CoV-2 pandemic. It pseudonymised data are linked to the range of data sets described above by NHS Digital, though usage must be approved on a study-by-study basis. It is one of the freshest (either daily or twice weekly data extracts) with data quality as good as it gets in primary care. The University of Oxford team run the national primary care surveillance system The Oxford-RCGP RSC. This surveillance system is sponsored by PHE and collaborates in reporting vaccine uptake and effectiveness, including of COVID-19 vaccine.

Additionally, the data on SARS-CoV-2 variants will be requested from the COG UK (Time lag – unknown).

Most individual data sources have frequent refresh (daily or weekly) and most have only 1–2-week lag from the time of data entry to when they are ready for analysis. One exception is the HES data source with the longest lag time of approximately 8-10 weeks. The raw hospitalization data source, SUS, which is the source of HES has much shorter time lag of 1-2 weeks. For this reason, our main analysis will include HES data until 8 weeks before the database lock. The sensitivity analysis will include HES data until 8 weeks before database lock.

Validation exercises will be conducted in the NHS Digital TRE, these are to ensure there is no denominator inflation and also to validate the GDPPR variables, as there are a limited number of concepts available. We will ensure the total population denominator is correct. The denominator varies across data sources therefore we will explore any areas of apparent list inflation. In addition, we will validate variables with a recorded prevalence in NHS Digital TRE within 15% of that in ORCHID, and validate or provide a surrogate marker for variables with >15% variation. Finally, we will choose and validate a multimorbidity measure ideally CMMS, but will consider using an alternative comorbidity measure if needed. The method for this exercise will be referenced in the Statistical Analysis Plan (SAP).

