The Hospital Episode Statistics (HES), Secondary Uses Service (SUS), General Practice Extraction Service data for pandemic planning and research (GDPPR), and Office of National Statistics (ONS) data may include information on COVID-19 infection through specific COVID-19 diagnosis codes. Using a combination of both COVID-19 SGSS/NPEX and diagnosis codes from HES, SUS, GDPPR, and ONS allow capturing the COVID-19 infection status for all study participants. Since testing for COVID-19 and its capture was not complete at the beginning of the pandemic but significantly improved later, restriction of the study period from July 2020 or the 2nd wave of infection by regions in England, whichever is later, for determining COVID-19 related events in the historical population is needed. Medically attended COVID-19 will come from ORCHID, GDPPR, Emergency Care Data Set (ECDS) and HES. Emergency department visits will come from ECDS. SARS-CoV-2 variants will come from COG UK. Data on HCRU and associated cost will come from HES using the Health Resource Grouper (HRG) and primary care attendance and medication costs. Long COVID will come from ORCHID and HES.

|--|

Variables		Data source	Comments
Hospitalization	Date	HES for curated data	6-8 weeks lag for HES
	Frequency	SUS for more recent raw data	SUS is updated weekly
	Duration	HES APC for combined	with a maximum of 2 weeks lag
ICU admission	Date	CC for ICU specific data	
	Frequency		
	Duration		
Death	Date	ORCHID/GDPPR for date	2 weeks lag
	Cause of death	ONS for cause of death	6 weeks lag
Medically attended COVID-19		ORCHID, GDPPR, ECDS, HES	
COVID-19 infection	Positive RT-PCR test; date	SGSS for first positive test in hospital and community NPEX for all positive/negative test in the community	Daily update
	ICD-10/SNOMED codes for COVID	HES, ONS, GDPPR	
SARS-CoV-2 variants of interest		COG UK	
Long COVID		ORCHID, HES	
HCRU and cost		HES & HRG	
		ICU datasets	
		Primary care attendance & costs	

APC: Admitted Patient Care; CC: Critical Care COG UK: COVID Genomics UK Consortium; ECDS: Emergency Care Data Set; GDPPR: General Practice Extraction Service data for pandemic planning and research; HES: Hospital Episode Statistics; HRG: Health Resource Grouper; ICU: Intensive Care Unit; NPEX: National Pathology Exchange; ONS: Office for National Statistics; ORCHID: Oxford-Royal College of General Practitioners Clinical Informatics Digital Hub; SGSS: COVID-19 Second Generation Surveillance System; SUS: Secondary Uses Service.

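### The hospital data cut is inconsistent: 9.4 gives main and sensitivity analyses the same cut, SUS cannot extend the national cohort, and the HES lag has three values

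*Protocol*

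**What the plan says.** Section 9.4 explains that HES is slow and that SUS, the raw feed behind it, is fast. It then sets the cut for the main analysis: "our main analysis will include HES data until 8 weeks before the database lock". The next sentence sets the cut for the sensitivity analysis: "The sensitivity analysis will include HES data until 8 weeks before database lock". SUS appears in neither.

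Section 9.7.1 refers back to 9.4 but describes something else. The primary analysis takes HES to 8 weeks before lock and then "all raw hospitalization data (SUS) from 8 weeks to 2 weeks prior database lock". The contrast is explicit: "A sensitivity analysis including only HES data, therefore a shorter follow-up for hospitalization, will also be done". Section 9.7.3 also lists the HES-only analysis, for hospitalization and ICU admission, as a sensitivity analysis.

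On linkage, the SUS entry in 9.4 ends: "Only available for linkage to ORCIHD". The ECDS entry carries the same restriction. The synopsis puts ORCHID at 18 million people, over 30% of England. Section 9.1 draws the effectiveness analyses from both ORCHID and the NHS Digital environment, and section 9.5 rests study size on the national database.

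On lags, Table 5 in section 9.3.2 gives "6-8 weeks lag for HES". The HES entry in 9.4 reads "Data on cost will be extracted from HES using HRG. (Time lag 8-12 weeks", and the closing text of 9.4 puts it at roughly 8 to 10 weeks. For registered cause of death, Table 5 gives 6 weeks, while 9.4 says "Time lag 8-12 weeks, released by NHS Digital with HES".

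**The concern.** The end of data capture for hospitalization and ICU admission, two of the three primary outcomes, has two definitions in current text. If 9.4 is followed literally, the HES-only sensitivity analysis repeats the main analysis and tests nothing. If 9.7.1 is followed, the rule calls for a feed that most of the national population does not have, and nothing limits that segment to ORCHID. In either case the HES cut may fall before the data are complete.

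Section 9.2.4 ends follow-up at the end of the study without a date for each outcome or dataset, so it does not settle the question. The quantities exposed are those without a ratio to protect them: the event rates that 9.7.1 promises for every outcome, the cumulative hospital use and costs at 1, 3 and 6 months in 9.7.6.2, and estimates for the latest calendar period. Section 9.12 plans monthly refreshes and interim analyses, so the ambiguity would return at each lock.

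**Working it through.** The protocol gives no figure to reproduce here. The check compares the passages and uses simple subtraction.

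**1. The two definitions of the cut**
- 9.4, main: HES to 8 weeks before lock. Sensitivity: HES to 8 weeks before lock. Difference: none.
- 9.7.1, primary: HES to 8 weeks, then SUS to 2 weeks. Sensitivity: HES only. Difference: 8 − 2 = 6 weeks of follow-up.
- 9.7.3 agrees with 9.7.1 on the HES-only sensitivity analysis.
- The end of primary hospital follow-up therefore differs by 6 weeks between 9.4 and 9.7.1.

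**2. Whether the SUS segment can be run**
- Timing: SUS lag is 1 to 2 weeks (9.4) and the segment ends 2 weeks before lock, so there is no shortfall.
- Coverage: 18 million at 30% implies 18 / 0.30 = 60 million. ORCHID is stated as over 30%, so the share without SUS linkage is at most about 1 − 0.30 = 70%.
- For those people the 9.7.1 primary analysis collapses into the HES-only analysis.

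**3. Whether HES is complete at the 8-week cut**

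Weeks before the cut that may be incomplete = max(0, stated lag − 8):
- Table 5, 6 to 8 weeks: 0.
- 9.4 closing text, 8 to 10 weeks: 0 to 2.
- 9.4 HES entry, 8 to 12 weeks: 0 to 4.

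The cut is the upper bound of the lag in Table 5 but the lower bound of both lags in 9.4.

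**4. Cause of death**
- The ONS lag is 6 weeks in Table 5 and 8 to 12 weeks in 9.4, and neither 9.4 nor 9.7.1 sets a cut for it.
- Date of death has a 2-week lag (Table 5). Section 9.3.2 also counts an event within 28 days of a positive RT-PCR as COVID-19 related. Only deaths identified through the coded cause are delayed.

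**5. Effect on the estimates**
- VE is 1 − RR. If capture in the last weeks is equally incomplete in both arms, the loss largely cancels in the ratio but not in the rates.
- Equal capture is not guaranteed everywhere. Section 9.7.1 allows matching on NHS region in place of practice, so a pair could have one member inside ORCHID and one outside it.

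**The case against.** The strongest reply is that the sentence in 9.4 is a slip. The text has just introduced SUS as the faster feed and gives that as its reason for the cut, so a phrase about SUS was probably dropped. Sections 9.7.1 and 9.7.3 together give a distinct and coherent pair of analyses. That is fair, and it makes the first part of the point a correction of wording. It does not answer the linkage restriction, which applies to the 9.7.1 version, or the conflicting lags.

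A reader might go further in four ways that the protocol does not support.

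- *That the hospital analysis cannot be carried out.* HES plus SUS can be run within ORCHID, and HES alone can be run nationally. What is missing is a statement of which cut applies to which dataset.
- *That national rates are understated by a calculable percentage, because person-time is counted in weeks with no admission feed.* No passage says that people without SUS linkage are followed past the HES cut. The wording of 9.7.1 points the other way: with HES alone, follow-up is shortened to match. Any percentage would also depend on a lock date and a distribution of person-time that are not shown.
- *That recent COVID-19 deaths are missed.* Death dates arrive within 2 weeks through ORCHID and GDPPR, the latter covering all practices in England, and SGSS test results arrive in under a week. The 28-day route therefore still works.
- *That the 8-week cut is too early on every figure given.* Under Table 5 it is adequate. The protocol does not show which lag is correct.

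**Conclusion.** The point holds as an inconsistency in how the primary hospital data are cut. Three statements need reconciling: identical cuts in 9.4 against different ones in 9.7.1 and 9.7.3, a difference of 6 weeks of follow-up; a SUS extension that 9.4 makes unavailable for up to about 70% of England; and a HES lag with three values, two of which leave up to 2 or up to 4 possibly incomplete weeks before the cut. The ONS cause-of-death lag has two values and no cut.

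This is more than detail left to the statistical analysis plan, because the passages conflict and the primary rule in 9.7.1 cannot be applied as written to the national dataset. The likely effect on the primary VE estimates is small, provided capture is equal in both arms. Absolute rates, hospital use and costs, and the most recent period are more exposed. The size of any undercount cannot be derived from the protocol.

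**What to change.** - Correct the two closing sentences on the cut in 9.4 so that they match 9.7.1 and 9.7.3: primary analysis HES then SUS, sensitivity analysis HES only.
- Reconcile Table 5 and 9.4 to one lag per source. Set the cut for HES, ICU and coded cause of death at or beyond the maximum reconciled lag. That is 12 weeks if the 8 to 12 week figure stands.
- State that the SUS extension, and outcomes based on ECDS visits, apply to ORCHID only. Start the SUS segment at the HES cut, wherever that falls, so that no gap opens between them.
- In the national cohort, end follow-up for hospital and ICU outcomes at the HES cut, and say so in 9.2.4.

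The cost is wording and a set of administrative censoring dates, plus some national follow-up at each lock. If the cut moves to 12 weeks, the loss is 12 − 8 = 4 weeks against the present HES cut, or 12 − 2 = 10 weeks against the end of follow-up that 9.7.1 implies with SUS. Later locks recover those weeks as HES fills in.
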